14.6.2. Missing Data

Subject-level listings will present data as reported. Missing or partially missing dates that are required for date-dependent definitions (eg, treatment-emergent AEs, concomitant medications) will be assumed to be the most conservative date possible. For example, an AE with a completely missing start date will be considered treatment-emergent; similarly, an AE that started the same month and year as IP administration but with missing start day will be considered treatment-emergent.

Multiple imputation methods will be used for missing observations for the primary efficacy endpoint, if required to prevent subjects from being excluded entirely from analysis.

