13.2.2. Relationship to Investigational Product

The Investigator will assess the relationship (causality) of an AE to the investigational product and administration procedure.

Causality will be defined as follows:

- **Probable:** adverse events that, after careful medical evaluation, are considered with a high degree of certainty to be related to the investigational product or administration procedure. The following characteristics will apply:
 - A reasonable temporal relationship exists between the event and the investigational product or administration procedure, and
 - The event is a known reaction to the investigational product or administration procedure, which cannot be explained by an alternative etiology commonly occurring in the population/individual.
- **Possible:** adverse events that, after careful medical evaluation, do not meet the criteria for a probable relationship to the investigational product or administration procedure, but for which a connection has reasonable certainty. The following characteristics apply:
 - The event occurs after exposure to the investigational product or administration procedure, and

- The event is not a known reaction to the investigational product or administration procedure, but cannot be explained by a commonly occurring alternative etiology, or
 - In the absence of a temporal relationship, the event cannot reasonably be explained by an alternative etiology.
- ***Unlikely***: adverse events that, after careful medical evaluation, do not meet the criteria for possible or probable relationship to investigational product or administration procedure and for which a connection is unlikely. The following characteristics will apply:
 - The event does not follow a reasonable temporal sequence from administration of the investigational product or administration procedure, or
 - May be explained by commonly occurring alternative etiology in the population/individual, or
 - May have been produced by environmental factors, and there is no apparent pattern of response to the investigational product or administration procedure.

An adverse event will be reported as “related” when causality is evaluated by an Investigator as probably or possibly related to the investigational product and/or the administration procedure. Related adverse events indicate a potential cause-and-effect relationship between the investigational product and/or administration procedure and the occurrence of the adverse event.

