13.2.4. Reporting Adverse Events

All adverse events are collected from the time of signing informed consent for trial participation until completion of 12 months or early termination, whichever occurs first. All AEs occurring after the initiation of the IV catheter placement for the initial dose of IP will be considered treatment emergent. Any ongoing adverse event that has not been resolved at the time of trial completion or early termination for a subject will be marked as ongoing on the adverse event case report form (CRF).

All AEs will be entered into the electronic data capture (EDC) system by trained site personnel at the investigative site.

Expected and unexpected SAEs must be reported to Capricor and entered into the EDC system within 24 hours of discovery of the event. For events that do not have complete information available at the time of initial report, the investigative site will submit all available information at the time of the submission. All SAE Report Forms must be signed by an Investigator and submitted with available source documentation. All source documentation must be de-identified prior to submission.

Should access to the EDC system be unavailable, SAEs and subsequent follow-up information must be reported to Capricor, or designee, via:

- Email: [REDACTED]
- Fax: [REDACTED]

All SAEs must be reported to the respective IRB in accordance with the investigative site’s policies. Copies of the submission will be collected by Capricor.

All SAEs will be reported to the DSMB at least semi-annually, or more frequently at the discretion of the Medical Monitor.

Capricor will promptly upon discovery, report serious and unexpected adverse events for which there is a reasonable possibility that the investigative therapy (i.e. administration product and/or investigative product) caused the events, to the Food and Drug Administration (FDA) in accordance with 21 CFR 312.32 regulations and ICH E2A guidelines.

For trials conducted under an investigational new drug (IND) application, FDA regulations require reporting of any serious suspected adverse reaction that is unexpected according to the current Investigator’s Brochure. A serious adverse reaction is defined as any adverse event for which there is a reasonable possibility that the drug/biologic caused the AE. For the purposes of IND safety reporting, “reasonable possibility” means there is evidence to suggest a causal relationship

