4.3 Handling of Dropouts or Missing Data

Subject-level listings will present data as reported. Missing or partially missing dates that are required for date-dependent definitions (e.g., treatment-emergent adverse events (TEAEs), concomitant medications) will be assumed to be the most conservative date possible.

For the primary efficacy endpoint, no imputation will be performed and the mixed-model repeated measures (MMRM) analysis will use all available data to estimate the mean treatment effect.

An AE with a completely missing start date will be considered treatment-emergent; similarly, an AE that started the same month and year as IP administration but with missing start day will be considered treatment-emergent.

AEs with missing seriousness will be counted as “serious” in tables and missing in listings; likewise, AEs with missing severity will be counted as “severe” in tables and missing in listings, and AEs with missing relatedness to the IP and/or IP administration procedure will be counted as “possible” and missing in listings.

Medical history with missing stop dates will be considered ongoing. Medications with missing stop dates will be considered in concurrent use during the study and counted in the summary table of concomitant medications unless the start date is after the last IP administration.

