7.1 Adverse Events

AEs will be coded using MedDRA coding system (Version 21.0). Potential primary safety endpoints, described in Section 2.2.1, will be adjudicated by an independent Clinical Events Committee (CEC).

The following AEs are defined as treatment-emergent AEs (TEAEs):

- AEs occurring after the initiation of the IV catheter placement for the initial dose of IP; or
- AEs with completely missing start date, or similarly, AEs that started the same month and year as IP administration but with missing start day.

Subject listings of all adverse events as reported will be provided. A separate listing will be done for TEAEs as adjudicated by the CEC. Serious AEs, primary safety endpoints as adjudicated, TEAEs adjudicated as related to IP or administration procedure, and hypersensitivity reactions as adjudicated will be listed separately.

All summary tables will be reported using TEAEs as adjudicated by the CEC. A summary of the primary safety endpoints will be presented. In addition, TEAEs related to IP or administration procedure and hypersensitivity reactions will be summarized.

AEs will be displayed by MedDRA SOC and PT, with subjects who have the same AE counted only once for that event and subjects who have more than one AE within a SOC counted only once in that SOC. The numbers and percentages of subjects reporting an event, as well as the number of events that were reported, will be calculated by treatment group.

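### The missing-start-date rule for adverse events ignores the stop date, so an event recorded as ending before the first infusion can be classed as treatment-emergent

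*Protocol*

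**What the plan says.** **Missing start dates.** Protocol 14.6.2 sets a general principle for missing or partial dates: each "will be assumed to be the most conservative date possible". As an example it adds that "an AE with a completely missing start date will be considered treatment-emergent", and it treats an AE with a missing start day in the month of IP administration the same way. SAP 4.3 gives both rules without the words that mark them as examples. SAP 7.1 then lists "AEs with completely missing start date, or similarly, AEs that started the same month and year as IP administration but with missing start day" as a TEAE criterion, joined by *or* to the criterion of occurring after catheter placement.

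**What a TEAE is in substance.** Protocol 14.4.2 requires that the event was absent before line placement, or was present and then worsened. Protocol 13.2.4 ties treatment emergence to occurrence after IV catheter placement for the first dose.

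**Relatedness.** SAP 4.3 says that "AEs with missing relatedness to the IP and/or IP administration procedure will be counted as" possible. Protocol 13.2.2 reports an AE as related when "causality is evaluated by an Investigator as probably or possibly related to the investigational product and/or the administration procedure". Related TEAEs are a primary safety endpoint (Protocol 7.2.1, SAP 2.2.1).

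**Pre-dose collection.** Protocol 13.2.4 states: "All adverse events are collected from the time of signing informed consent for trial participation". Table 3 marks AE assessment at Screening and Baseline. Protocol 14.4.2 limits collection from consent to SAEs.

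**The concern.** A default for missing dates should settle cases where the timing is unknown. Here it also applies where the timing is known. If an AE has no start date but its stop date precedes the first catheter placement, it must also have started before placement, yet the rule still classes it as treatment-emergent. The plan therefore gives two answers for the same event: a TEAE under SAP 7.1, and not a TEAE under Protocol 14.4.2 and 13.2.4.

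What is at stake is mainly the TEAE count. If relatedness is blank as well, a primary safety endpoint is affected. In a trial of 20 subjects, one subject counted wrongly makes a visible difference to a percentage.

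**Working it through.** The documents give no figure for this rule, so there is none to reproduce. The check has two parts: apply the rule to the possible cases, then size one misclassified subject.

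**Step 1: apply the rule.** Inputs are the TEAE criterion in SAP 7.1, the relatedness default in SAP 4.3, and the mapping of possible to related in Protocol 13.2.2. The start date is missing in every row, and first placement is on Day 1.

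| Stop date | Relatedness recorded | TEAE as written | Related TEAE as written | Related TEAE with a stop-date check |
|---|---|---|---|---|
| Day -10 | missing | yes | yes | no |
| Day -10 | unlikely | yes | no | no |
| missing | missing | yes | yes | yes |
| missing | unlikely | yes | no | no |
| Day 20 | missing | yes | yes | yes |
| Day 20 | unlikely | yes | no | no |

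A stop-date check changes the related-TEAE result only in the first row. In the second row it changes the TEAE class but not the primary endpoint. The four rows with a missing or post-dose stop date do not change, so the rule stays conservative where timing really is unknown.

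**Step 2: compare the first row with the plan's definitions.** The event ended before placement, so it fails both parts of the TEAE definition in Protocol 14.4.2 and the timing in 13.2.4. It also conflicts with a characteristic that Protocol 13.2.2 lists for a possible relationship: "The event occurs after exposure to the investigational product or administration procedure".

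**Step 3: size of one misclassified subject.** SAP 3.1 gives 20 randomized subjects and 1:1 allocation. Actual arm sizes are not stated, so 10 per arm is an assumption, with 8 to 12 as the range. Incidence counts subjects, so the shift for one subject with no other related TEAE is 100/n percentage points:

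- n = 8: 100/8 = 12.5
- n = 10: 100/10 = 10.0
- n = 12: 100/12 = 8.3

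For 0 of 10, the exact (Clopper-Pearson) 95% upper limit is 1 − 0.025^(1/10) = 30.8%. For 1 of 10 it is 44.5%.

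**Step 4: conditions for reaching the primary endpoint.** Three must hold together: an incomplete start date covered by the rule, a recorded stop date before first placement, and missing relatedness. The TEAE count needs only the first two.

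**The case against.** The case on the other side is substantial.

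- **The governing principle.** The protocol's rule is an example of taking the most conservative date *possible*, and a start after a known stop is not possible. With 14.4.2, this supports reading a stop-date check into the plan. That stands as one reading. SAP 7.1, however, makes the missing date a criterion of its own without that qualification, and literal programming would follow it.
- **Adjudication.** Potential primary safety endpoints go to a blinded CEC, which can change a report to a non-AE (SAP 7.1.1), and SAP 7.1 bases summary tables on adjudicated TEAEs. This is a real safeguard, but an incomplete one. Nothing directs the CEC to reclassify by stop date, and a genuine screening event is still an AE, only not treatment-emergent. Addendum 3.1 then summarises raw TEAEs and only lists the adjudicated data.
- **Few pre-dose events.** If 14.4.2 governs, only SAEs are collected before dosing, and these are reported within 24 hours on signed forms. Protocol 13.1.3 sends clinically significant pre-dose examination findings to medical history. This may shrink the pool but does not empty it.
- **Blank relatedness.** A reader might infer that this field will usually be empty for pre-dose events. The documents do not support that: Protocol 13.2.3 requires a causality assessment for each AE, and queries and monitoring are aimed at missing data.
- **Direction.** The rule can only over-count, applies to both arms, and feeds no formal test (Protocol 14.4). All of this stands and keeps the point minor.

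**Conclusion.** The gap is real and minor. As written, SAP 7.1 and 4.3 class an AE as treatment-emergent even when its own stop date shows that it ended before first placement, which contradicts Protocol 14.4.2 and 13.2.4. Entry to the related-TEAE endpoint also requires missing relatedness.

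On the assumption of 10 per arm, and for a subject with no other related TEAE, one such event moves an arm's incidence by 10 percentage points (8.3 to 12.5 for arms of 12 to 8). The number of such events is not known and may be zero.

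Two stronger conclusions are not supported. A reader might infer that pre-dose events will regularly reach the primary safety endpoint, but that needs all three conditions together and no adjudication that removes the event. A reader might also take the length of the pre-dose collection window, relative to total follow-up, as an error rate. It is only a ratio of window lengths and says nothing about how often dates are missing.

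**What to change.** In SAP 4.3 and 7.1, add to the missing-start-date rule: *unless the recorded stop date (complete, or partial but sufficient) is before the first IV catheter placement, in which case the AE is not treatment-emergent*. AEs with a missing, ambiguous or post-placement stop date remain TEAEs. The example in Protocol 14.6.2 can stay, because the SAP supplies the detail.

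Reconcile Protocol 13.2.4 (all AEs from consent) with 14.4.2 (SAEs only), so that it is clear which pre-dose events the database should hold.

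Two other changes might suggest themselves but would not help. The date on which an event was first recorded does not show that it ended before dosing. Restricting the relatedness default to TEAEs leaves this endpoint unchanged, because it already counts only TEAEs.

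The cost is one clause in each of two SAP sections, one programming condition, and a clarification of the collection rule. TEAE counts can only stay the same or fall, and only for events shown to have ended before dosing.

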14.6.3. Interim Analysis for Futility

The pre-specified interim analysis was performed. Following the interim analysis, further enrollment in the trial was terminated. No further interim analyses are planned.

15. TRIAL OVERSIGHT

15.1. Steering Committee

The Steering Committee will provide the overall scientific direction for the trial. The responsibilities of the Steering Committee are to: (a) maintain contact with trial Investigators to ensure high quality data collection; (b) approve and implement major protocol changes; (c) collaborate in data analysis, interpretations, and publications; (d) establish criteria for authorship on all manuscripts, publications and presentations that arise from the trial.

15.2. Clinical Events Committee (CEC)

The purpose of CEC adjudication is to provide consistent and unbiased adjudication of clinical outcomes and specified events through the independent review of source documentation. The charge of the CEC is to review source documents and to adjudicate the classifications of all potential primary safety endpoint events. Sites will be provided instructions in the MOP on how to collect and submit event information required for CEC review. The CEC will remain blinded to subject treatment assignments. The individuals that serve on the committee will be appointed by Capricor, are independent from all other trial activities, and are not affiliated with any investigative site. The committee will consist of, at a minimum, a neurologist and pulmonologist with experience in treating patients with DMD. Additional experts in immunology will be consultants to the committee as necessary. The frequency of CEC meetings is detailed in the CEC Charter.

15.3. Data Safety Monitoring Board

To meet the trial's ethical responsibility to its subjects, an independent Data Safety Monitoring Board will monitor results during the trial. The board consists of physicians and biostatistician(s) appointed by Capricor, who have no formal involvement or conflict of interest with the Investigators, investigative sites, subjects, or Capricor. The DSMB will act in a senior advisory capacity to Capricor regarding data and safety matters throughout the duration of the trial. The board will meet on a periodic basis according to the DSMB charter to monitor the available information regarding safety, efficacy, and quality of trial conduct. The DSMB will communicate their recommendations directly to Capricor. The investigative sites will have no contact with the members of DSMB and no voting member of the committee may participate in the trial as an Investigator.

16. SOURCE DATA AND TRIAL DOCUMENTS

16.1. Electronic Data Capture

All trial data will be entered into the EDC system. Site personnel requiring access will have their own Login/Password. Access to trial information will be based on individual roles and responsibilities. The application employs fine-grained role-based access control for data entry, viewing and reporting options. All trial data will be transmitted over an encrypted SSL (Secure Sockets Layer) connection that requires user authentication.

This application is designed to be in full compliance with the International Conference on Harmonization and Good Clinical Practices (ICH-GCP), the FDA's CFR 21 Part 11 Electronic Record and Electronic Signatures, the FDA's "Guidance: Computerized Systems Used in Clinical Studies," and Health Insurance Portability and Accountability Act (HIPAA).

EDC supports efficient data collection and management and facilitates rapid data closure. A strong advantage of web-based design is that Capricor, or designee, has immediate access to the data from all investigative sites so that queries can be generated and distributed to the sites in real-time and the frequency of missing data can be reduced.

16.2. Trial Monitoring

In accordance with 21 CFR 312.56, ICH- GCP, and local regulations, trial monitors will periodically complete on-site monitoring of data with a focus on safety, trial endpoints, data completion, data outliers and data integrity. Trial monitors will schedule an on-site visit with a site coordinator for an appropriate duration based on the scope of data anticipated to be collected. Prior to the visit, a confirmation letter will be sent to the investigative site, which will include a listing of which CRFs and source documents will be reviewed.

Site coordinators are to have all source documents up to date and easily accessible to a monitor.

During an on-site monitoring visit, trial monitors are to:

- Track the overall monitoring process including data collected and entered, visit schedules, and subject screening and enrollment.
- Verify and ensure compliance with the protocol according to GCP and HIPAA requirements.
- Ensure that appropriate data corrections are made, dated, explained, and initialed by the Investigator or representative.
- Assess the impact of any personnel changes on the investigative site's ability to conduct the trial.
- Verify a minimum of the following data points for all subjects: date of birth, signed informed consent, eligibility criteria, medical history, date of enrollment, serious AEs, and mortalities.
- Perform review of informed consent process and review documentation of informed consent for completeness and correctness.

- Perform on-site validation checks of recoded data by reviewing source documents to determine whether the data reported in the EDC system are complete and accurate. Source documents include medical charts, screening records and/or logs, research procedure records and/or files, and other trial related notes.
- Monitor subject safety by verifying that any AE, therapy modification, or concomitant medications are reported in accordance with the protocol.
- Determine whether all AEs, protocol deviations, and protocol violations are appropriately reported within the required time periods according to applicable regulatory requirements as outlined in the protocol and by regulatory agencies.
- Verify that any missed visits, tests, and examinations that were not performed, as well as trial withdrawals and/or dropouts are explained and clearly reported.
- Inform the site PI about any deviations from or violations of the trial protocol, GCP and/or regulatory requirements in order for appropriate actions to be taken to prevent recurrence of the deviation and/or violation.
- Inform the Investigator of any major data entry error, delays in data entry, omissions, or eligibility requirement errors.
- Verify that regulatory documentation is accurate, complete, current, and properly maintained.
- Verify that PI oversight of trial conduct is documented via signature or initials and date on documentation regarding eligibility, AEs, and abnormal laboratory values.

The monitor may also inspect the investigative site's facilities to verify that proper space for study documents, equipment and investigational product is available.

A debriefing meeting with the PI, site coordinator(s), and the Monitor to review any notable findings will be scheduled toward the end of the on-site visit. The monitor will submit a written monitoring visit report to Capricor and send a follow-up letter with findings to the PI. The report and letter will include a summary of documentation reviewed by the monitor, any significant findings, AEs, protocol deviations and violations, missing regulatory documents and actions taken, to be taken or recommended to ensure compliance. The report and letter will include a list of action items. Investigative sites are expected to complete the list of actions items within 30 days of receipt.

